7.4 Pre-Specified Subgroup Analyses

We will examine variation in the intervention effects on the change in BPI within clinical subgroups defined by presence or absence at baseline of the subgroup status/conditions described above. For each subgroup measure, we will fit a repeated-measures linear regression modelling change from baseline in BPI at the quarterly follow-up assessments using assigned intervention, assessment point, subgroup indicator and all interactions between these three measures together with baseline BPI score and its interaction with assessment point as explanatory measures. Assessment points will be incorporated as random effects, with an unstructured covariance, to model potential correlation among outcomes for individuals. Our primary assessment of an interaction between intervention and the subgroup measure will use the model-based two-sided Wald test for an interaction at the 12-month assessment, using a 0.005 significance level. Weighted selection model analyses similar to those described above will examine sensitivity of 12-month results to response biases.

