7.1.2 Subgroup power estimates

A difference of 1 unit in BPI is considered clinically significant and the SD of the BPI scores is typically about 2 units. A sample size of 776 participants at the 12-month

assessment will provide $> 80\%$ power for detecting a clinically meaningful difference in intervention effects across subgroups with prevalence of at least 40%, assuming a Bonferroni corrected significance level of 0.01. For a 1.2-unit difference in intervention effects, the study will have $> 85\%$ power for subgroup prevalence of 25% or more. Within a subgroup, the study will have $> 80\%$ power to detect an intervention effect of 1 unit or more for subgroup prevalence of $> 25\%$ and a 0.01 significance level. These power calculations for comparisons of 12-month outcomes consider just the data for this assessment point as a worst-case scenario. The repeated measures analyses discussed below should have power greater than discussed here for comparing the 12-month outcomes. Based on preliminary data, we anticipate the proposed sample size will provide adequate power for planned assessments of the HTE for all planned subgroups; if prevalence of any subgroup is $< 25\%$, assessment of HTE across subgroups will be exploratory.

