7.5 Secondary Analyses and Analysis of Secondary Outcomes

If the proportion of patients in the standard options arm achieving the 50% dose reduction outcome falls in the range 20%-70%, the anticipated sample size will provide 80% power to detect between-group differences in the range of 14 and 17%. The study will have this same level of power for comparable differences in the proportions achieving a 25% dose reduction and proportions with any dose reduction. We will have 80% power for assessing small to moderate differences of 0.35 SD in mean dose change.

The secondary dose escalation outcome is defined as a proportional increase in daily dose of $\geq 25\%$ from baseline to 12 months. If 5-15% of participants meet this dose escalation outcome, we will have 80% power to detect between-group differences of 7-8%.

In addition, we will assess between-group differences in the pain-related function, pain intensity, quality of life, fatigue and sleep, mental health measures, and physical symptoms over the follow-up period. We will fit separate repeated-measures linear regressions modelling change from baseline at the follow-up assessments using assigned intervention, assessment point and their interaction together with the respective baseline score and its interaction with assessment point as explanatory measures. Assessment points will be incorporated as random effects, with an unstructured covariance, to model potential correlation among outcomes for individuals. The primary assessment of an intervention effect on a particular outcome will use the model based 2-sided Wald test for a difference at the 12-month assessment together with the point and confidence interval estimates for the mean difference in change from baseline.

We will examine variation in effects by sex, study site and over the course of enrollment, as well as moderation of effects by relevant covariates. Analyses will be similar to the subgroup analyses described above.

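### The subgroup interaction test is set at 0.005 in section 7.4, but its power in section 7.1.2 was computed at 0.01

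*Combined protocol and SAP*

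**What the plan says.** Section 7.4 models change in BPI at the quarterly assessments. Its main test of each intervention-by-subgroup interaction "will use the model-based two-sided Wald test for an interaction at the 12-month assessment, using a 0.005 significance level". The model also adjusts for baseline pain, "together with baseline BPI score and its interaction with assessment point as explanatory measures".

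Section 7.1.2 gives the power for a difference in intervention effects between subgroups at 12 months, "assuming a Bonferroni corrected significance level of 0.01". With 776 participants it states more than 80% power for a 1-unit difference when prevalence is at least 40%, and more than 85% for a 1.2-unit difference when prevalence is 25% or more. Its SD assumption is that "the SD of the BPI scores is typically about 2 units". It says that the calculations "consider just the data for this assessment point as a worst-case scenario" and that the repeated-measures analyses "should have power greater than discussed here for comparing the 12-month outcomes". It concludes that "we anticipate the proposed sample size will provide adequate power for planned assessments of the HTE for all planned subgroups", with an exploratory label for any subgroup below 25% prevalence.

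The abstract and section 1.2.1 list five subgroups. Section 7.5 adds sex, site, enrollment time and other covariates as moderators, and says of them: "Analyses will be similar to the subgroup analyses described above".

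**The concern.** The two sections describe the same outcome (BPI), time point (12 months) and contrast (intervention by subgroup), but use different significance levels. The 0.01 has an evident source, 0.05/5. The 0.005 would follow from 0.05/10, but no section defines ten tests. Both levels stand in current text, not in the revision history.

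Two things are at stake. First, the adequacy conclusion in 7.1.2 rests on power computed at a looser level than the test to be run, so a reader of a null interaction result would credit it with more power than the stated basis supports. Second, an interaction p-value between 0.005 and 0.01 would fail the rule in 7.4 but pass the level used in 7.1.2. Section 7.4 is the operative rule, but leaving two levels in the plan invites debate once results are known. Four of the five subgroups carry a directional hypothesis in section 1.2.1, so these are not incidental analyses.

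**Working it through.** **Inputs**
- N = 776 at 12 months, which is 80% of 970 (sections 7.1 and 7.1.2).
- SD = 2 BPI units (7.1.2).
- Equal allocation to the two arms (4.3.9).
- Case A: difference δ = 1 unit, prevalence p = 0.40, stated power above 80%.
- Case B: δ = 1.2 units, p = 0.25, stated power above 85%.
- Two-sided critical values: 2.576 at 0.01 and 2.807 at 0.005.

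**Formulas**

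The interaction is a difference between two treatment differences, so with equal arms within subgroups:

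SE = √[ (4 · SD² / N) · (1/p + 1/(1−p)) ], and power = Φ(δ/SE − z).

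**Standard errors and effect ratios**
- Case A: SE = √[(16/776) · (1/0.40 + 1/0.60)] = 0.2931; δ/SE = 3.412.
- Case B: SE = √[(16/776) · (1/0.25 + 1/0.75)] = 0.3316; δ/SE = 3.619.

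**Reproducing the plan's figures at 0.01**
- Case A: Φ(3.412 − 2.576) = Φ(0.836) = 79.8%.
- Case B: Φ(3.619 − 2.576) = Φ(1.043) = 85.1%.

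Both match the stated figures to within rounding. A noncentral t calculation gives 79.6% and 85.0%.

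**Same inputs at the section 7.4 level, 0.005**
- Case A: Φ(3.412 − 2.807) = Φ(0.605) = 72.7%.
- Case B: Φ(3.619 − 2.807) = Φ(0.812) = 79.1%.

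These are about 7 and 6 points lower. For a 1-unit difference the best case is 50% prevalence, where power is 75.0%, so no prevalence reaches 80% on this basis.

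**Detectable difference**, SE · (z + z for the target power, 0.842 for 80% and 1.036 for 85%)
- Case A, 80% power: 1.00 unit at 0.01 and 1.07 at 0.005.
- Case B, 85% power: 1.20 units at 0.01 and 1.27 at 0.005.

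**Completers needed for the stated power**
- Case A: 779 at 0.01 and 888 at 0.005 (888/970 = 91.5%).
- Case B: 774 at 0.01 and 876 at 0.005 (876/970 = 90.3%).

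**Power at 0.005 under better conditions**

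Baseline adjustment multiplies the variance by 1 − ρ², where ρ is the correlation of 12-month with baseline BPI. The protocol gives no ρ, so the values here are assumptions.

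| Completers | ρ | Case A | Case B |
|---|---|---|---|
| 776 (80%) | 0 | 73% | 79% |
| 873 (90%) | 0 | 79% | 85% |
| 873 (90%) | 0.2 | 81% | 87% |
| 873 (90%) | 0.3 | 84% | 89% |
| 922 (95%) | 0 | 82% | 87% |

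With 776 completers, ρ of about 0.35 (case A) or 0.34 (case B) is needed to reach the stated power at 0.005.

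**The case against.** The strongest reply is that the figures in 7.1.2 are presented as a floor. They ignore the repeated measures and the baseline adjustment and assume only 80% retention, whereas section 7.2 reports completion above 95% in similar studies. At 95% retention, power at 0.005 is 82% and 87% with no gain from covariates. So the adequacy conclusion may well be true at 0.005. That stands, and it limits the consequence. It does not remove the mismatch: the caveat concerns how much data is used, not the significance level, and the protocol gives no figure at 0.005. At 90% retention without covariate gain, power is just short of both stated values.

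A second reply is that 0.005 may be a per-tail value, since a one-sided 0.005 test has the same critical value as a two-sided 0.01 test. But 7.4 says two-sided, so on that reading 7.4 is misworded and needs correcting.

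A third is that 0.005 may cover a wider family that takes in the moderators in 7.5 or the taper comparison in 7.6. Neither section says so, and 7.1.1 gives the Aim 2 taper comparison its own unadjusted 0.05. Family membership for those analyses is a clarification, not the core of this point.

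It is also fair to say that no calculation in 7.1.2 is wrong at its own level. The defect is an inconsistency between sections.

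**Conclusion.** The concern holds. The interaction power stated in 7.1.2 belongs to a two-sided 0.01 test, and the planned test in 7.4 is two-sided 0.005. On the worst-case basis that 7.1.2 adopts, power at the planned level is about 73% instead of over 80%, and about 79% instead of over 85%. These figures rest on 776 completers, an SD of 2, equal allocation and 12-month data without covariate gain. They are lower-end values, and actual power may reach the stated levels if retention is high or baseline BPI is moderately predictive.

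The consequence is confined to secondary subgroup analyses. The operative level is the stricter one, type I error is not inflated, and the primary 0.05 test and the enrollment target are untouched. It should be fixed, but it does not threaten the trial's main conclusion.

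**What to change.** State one significance level for the interaction tests, with the family it covers, in both 7.1.2 and 7.4. Either option is coherent:

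- **Keep 0.005.** Say which tests it covers, and restate the interaction power in 7.1.2 as about 73% (1 unit, 40% prevalence) and about 79% (1.2 units, 25% prevalence) on the worst-case basis. Any expected gain from retention or baseline adjustment can be added, with its assumptions.
- **Use 0.01.** If 0.05/5 was intended, change the level in 7.4 and give the power as about 80% and about 85%. The existing figures then hold apart from rounding: 79.8% against a stated value above 80%.

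A clause saying whether the moderator analyses in 7.5 and the taper analyses in 7.6 fall in the same family would be useful. The choice should be fixed and dated before outcome data are examined. The cost is one sentence and two figures, or one number in 7.4 with light edits to 7.1.2, and nothing operational.

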7.5 Secondary Analyses and Analysis of Secondary Outcomes

If the proportion of patients in the standard options arm achieving the 50% dose reduction outcome falls in the range 20%-70%, the anticipated sample size will provide 80% power to detect between-group differences in the range of 14 and 17%. The study will have this same level of power for comparable differences in the proportions achieving a 25% dose reduction and proportions with any dose reduction. We will have 80% power for assessing small to moderate differences of 0.35 SD in mean dose change.

The secondary dose escalation outcome is defined as a proportional increase in daily dose of $\geq 25\%$ from baseline to 12 months. If 5-15% of participants meet this dose escalation outcome, we will have 80% power to detect between-group differences of 7-8%.

In addition, we will assess between-group differences in the pain-related function, pain intensity, quality of life, fatigue and sleep, mental health measures, and physical symptoms over the follow-up period. We will fit separate repeated-measures linear regressions modelling change from baseline at the follow-up assessments using assigned intervention, assessment point and their interaction together with the respective baseline score and its interaction with assessment point as explanatory measures. Assessment points will be incorporated as random effects, with an unstructured covariance, to model potential correlation among outcomes for individuals. The primary assessment of an intervention effect on a particular outcome will use the model based 2-sided Wald test for a difference at the 12-month assessment together with the point and confidence interval estimates for the mean difference in change from baseline.

We will examine variation in effects by sex, study site and over the course of enrollment, as well as moderation of effects by relevant covariates. Analyses will be similar to the subgroup analyses described above.

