5.2 Common intervention elements

The TCM and IPT interventions share several common approaches and processes, including the following:

- Collaboration with primary care teams. During the study, TCM/IPT intervention clinicians will assume primary management of chronic pain care for patients enrolled in the study; however, both interventions are intended to supplement, rather than replace, primary care pain management. Intervention clinicians in both arms use structured CPRS templates to guide visits. Care management notes entered into CPRS are the primary method of communicating with the primary care team, consistent with usual practice in VA. If indicated by clinical or safety issues, clinical intervention teams will communicate directly with the patient's primary care or mental health team.
- Patient-centered informational materials. Patient-centered communication will be supported by development of informational materials. These materials will be used by clinicians in both intervention arms.
- Shared decision-making. Both arms will use a shared decision-making approach to guide pain treatment and opioid dose reduction. Shared decision-making is an approach to clinical decisions that involves bidirectional information exchange, interactional deliberation about options, and agreement on a course of action.
- Individualized opioid taper preparation. Clinicians in both intervention arms will manage pain with non-opioid therapies while assessing interest in and readiness for opioid dose reduction/discontinuation at each follow-up visit. When patients indicate interest in opioid dose reduction or in learning more about the process, detailed information about opioid tapering options will be provided. We anticipate participants will require a variable number of visits to develop readiness for opioid dose reduction/discontinuation, so timing of the process will be highly individualized. This approach allows patients time to establish trusting relationships and become more informed and activated.

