5.6.3 Buprenorphine rotation management

Decisions about how to initiate buprenorphine should be individualized, considering patient needs and preferences, as well as prescriber experience and local resources. Patients may initiate buprenorphine at home or in clinic. There are two methods for rotating from full-agonist opioids to buprenorphine: a traditional method and a newer method of microdose up-titration. In the traditional method, full-agonist opioids are stopped entirely prior to starting buprenorphine. Case series suggest that patients usually prefer tapering rapidly over 2-5 days, rather than discontinuing abruptly. The interval between last dose of the full-agonist opioid and the first dose of buprenorphine-naloxone depends on the duration of action of the full-agonist opioid. In most cases, 12-18 hours is appropriate for short-acting opioids. For long-acting opioids, a longer interval is typically needed, from approximately 18-24 hours for morphine SA to approximately 48-72 hours for methadone. Patients on methadone should first taper down to 30 mg daily dose of methadone, per standard protocol. Patients using the traditional rotation method are advised they will experience opioid withdrawal symptoms during the interval after stopping full-agonist opioids and before starting buprenorphine.

In the microdose up-titration method, buprenorphine is started at very low doses several days before the full-agonist opioid is stopped. Buprenorphine is up-titrated over several days (typically 3-5 days) and then the full-agonist opioid is discontinued once buprenorphine is at a therapeutic dose. Case series demonstrate that the microdose up-titration method is well-tolerated; in our clinical experience, some patients on long-term opioid therapy for pain prefer this approach because they do not have to experience opioid withdrawal symptoms before initiating buprenorphine.

Precipitated opioid withdrawal is the main potential adverse effect of buprenorphine-naloxone rotation; it is avoided if participants follow the initiation protocol. When using the traditional rotation method, the most critical point patients need to understand is that the "old" opioids must be out of their system before buprenorphine-naloxone initiation. This means they need to wait for the onset of at least moderate withdrawal symptoms.

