5.6.5 Buprenorphine visit schedule

The initial buprenorphine visit with the buprenorphine prescriber may occur by any mode allowable by current regulations, as described above, but face-to-face (i.e., in-person or video) is preferred. First visit tasks include the following:

- Obtain history of current opioid use; assess buprenorphine risk factors (including risk for pregnancy if applicable)
- Provide standardized buprenorphine educational materials and resources
- Use shared-decision making to determine whether to proceed with buprenorphine rotation
- Document visit on buprenorphine initial visit template

Following buprenorphine initiation, structured follow-up will occur at three time points: 2 days, 1 week, and 3 weeks after initiation. These visits may occur by telephone or face-to-face, as appropriate. Patients will be instructed on whom to contact for problems or concerns occurring between visits. After the three structured visits, follow up will occur according to the assigned TCM or IPT intervention. Most follow-up visits will occur by telephone, although participants will have the option of face-to-face visits. Follow-up visit tasks include the following:

- Assess medication response and adverse effects, including withdrawal symptoms as appropriate
- Administer standard satisfaction questions
- Provide additional education and counseling as needed
- Document visit on buprenorphine follow-up visit template

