10.4.1 Known risks of study interventions

Participants may experience adverse effects of pain medications prescribed in the course of the study. Medications are FDA-approved and have known adverse effects; benefits and risks of medication changes will be discussed with patients as in usual practice.

Patients may experience withdrawal symptoms and other temporary discomfort due to reducing opioid doses or switching from one opioid medication to another. Intervention clinicians will educate participants about withdrawal symptoms, take precautions to prevent withdrawal, and manage symptoms if they occur.

Participants may experience adverse effects of non-pharmacological pain management therapies recommended in the course of the study. Non-pharmacological therapies (e.g., yoga, home exercise programs, psychotherapy) have known adverse effects, most of which are mild and transient. Benefits and risks of recommended therapies will be discussed with patients as in usual practice.

10.4.2. Known risks and potential harms associated with the underlying condition or study population

All participants will have chronic pain and be on long-term moderate-to-high dose opioid therapy at baseline. Long-term opioid therapy is associated with physiologic adaptations, including tolerance, dependence, and a withdrawal syndrome. Opioids have serious known risks, including respiratory failure, opioid use disorder, and death. Higher doses of opioids are associated with greater risks of depressive disorder, opioid use disorder, respiratory failure, suicide, and overdose death.

Chronic pain typically has a fluctuating course characterized by intermittent episodes of symptom exacerbation and improvement.

The study population is also expected to have a substantial pre-existing burden of physical and mental health comorbidity.

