10.5.1.2 Assessment of treatment-related symptoms

Participants will be asked about medication related symptoms at each research assessment interview (3, 6, 9, and 12 months).

A checklist addressing common medication-related AE is incorporated into intervention follow-up note templates, along with an open field for reporting additional AE.

Symptoms recorded in note templates will be retrievable for summary reporting.

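### Patient-reported adverse symptoms are collected four times but judged primarily at month 12, which can miss a harm the plan calls temporary and individually timed

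*Combined protocol and SAP*

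**What the plan says.** **The harm.** Section 10.4.1 warns: "Patients may experience withdrawal symptoms and other temporary discomfort due to reducing opioid doses or switching from one opioid medication to another". Section 5.6.3 adds: "Precipitated opioid withdrawal is the main potential adverse effect of buprenorphine-naloxone rotation". Section 10.4 treats the rotation protocol as the only experimental treatment. On when tapers start, Section 5.2 says that "timing of the process will be highly individualized".

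**The data.** Section 1.2.2 lists adverse symptoms as a patient-reported secondary outcome. Table 2 (Section 6.2.3) schedules adverse effects at baseline and all four follow-ups, Section 6.2 has masked staff do the follow-up interviews, and Section 10.5.1.2 confirms the four symptom enquiries. After buprenorphine is started, "structured follow-up will occur at three time points: 2 days, 1 week, and 3 weeks after initiation" (Section 5.6.5), and the tasks at those visits include assessing withdrawal.

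**The analysis.** Section 7.5 covers "mental health measures, and physical symptoms over the follow-up period". It fits arm, assessment point and their interaction, and then names as the primary assessment of each outcome the "model based 2-sided Wald test for a difference at the 12-month assessment". Section 7.6 applies comparable testing to expanded against standard taper options. Section 7.7 compares hospitalizations, ED visits and SUD admissions at each time-point and overall, promises similar comparisons for other adverse events, and breaks them out by taper assignment. Its stated source is VA administrative data.

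**The concern.** The symptom interviews are the fairest evidence on harm in this open-label trial: assessors are masked and both arms follow the same schedule. The primary contrast uses one of the four visits. For a lasting difference that is a reasonable choice. For discomfort that comes with a dose change and then passes, month 12 shows only what is present in patients who changed dose shortly before it. An arm that causes more withdrawal on the way to a lower dose could be reported as showing no symptom difference.

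Two gaps in wording add to this. Section 1.2.2 speaks of adverse symptoms, Table 2 of adverse effects and Section 7.5 of physical symptoms. If these are not the same measure, Section 7.5 gives adverse symptoms no analysis. And Sections 7.5 to 7.7 do not mention the 2-day, 1-week and 3-week data, the only assessments timed to rotation.

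**Working it through.** **1. The plan's own figure.** The plan gives no power for symptoms. The nearest figure is Aim 2 (Section 7.1.1): 970 × 0.80 × 0.35 / 2 = 135.8 per taper group. At 135 per group and 0.35 SD, power = Φ(0.35 × √(135/2) − 1.96) = Φ(2.876 − 1.96) = 82%. The stated figure of more than 80% reproduces.

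**2. Dilution at month 12, taper comparison.** Assume that symptomatic patients score 1 SD worse and that a share f of one arm, and none of the other, is symptomatic at that visit. The mean difference is f SD and power is Φ(f × √67.5 − 1.96).

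| f | Difference (SD) | Power |
|---|---|---|
| 5% | 0.05 | 6% |
| 10% | 0.10 | 13% |
| 20% | 0.20 | 38% |
| 35% | 0.35 | 82% |

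**3. Month 12 against the four-visit average, main comparison.** From the plan: 776 / 2 = 388 per arm and visits at 3, 6, 9 and 12 months. Assumed, because the documents give none of it: 30% v 45% of patients taper; symptoms add 1.2 SD from taper start for D months; starts are spread evenly; correlation between any two assessments is 0.5; an interview detects only symptoms present at that time.

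- Let s be the share of tapering patients symptomatic at a visit. The arm difference is (0.45 − 0.30) × 1.2 × s = 0.18 s.
- Baseline-adjusted residual variance is 1 − 0.5² = 0.75 at one visit. For the mean of four it is (1 + 3 × 0.5)/4 − 0.5² = 0.375.
- For an arm with tapering proportion q, the mixture adds 1.44 × qs(1 − qs) at one visit, and 1.44 × [q E(m²) − (q E(m))²] for the mean, where m is the fraction of the four visits at which a tapering patient is symptomatic.
- Power = Φ(δ/SE − 1.96) + Φ(−δ/SE − 1.96).

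Example, starts in months 1 to 9 and D = 3. Shares at months 3, 6, 9 and 12 are 2/8, 3/8, 3/8 and 0, with mean 0.25. At month 12, δ = 0, so power is the 5% test level. For the average, δ = 0.18 × 0.25 = 0.045. Every tapering patient is symptomatic at exactly one visit, so the mixture term is 0.09 q(1 − q), and SE = √((0.3939 + 0.3973)/388) = 0.0452. Then δ/SE = 1.00 and power is 17%.

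| Starts (months) | D (months) | s at month 12 | Mean s | Power, month 12 | Power, average |
|---|---|---|---|---|---|
| 1–9 | 3 | 0% | 25% | 5% | 17% |
| 1–9 | 4 | 12.5% | 34% | 6% | 26% |
| 1–9 | 6 | 37.5% | 50% | 17% | 46% |
| 1–12 | 3 | 27% | 25% | 11% | 17% |
| 1–12 | 1 | 9% | 9% | 6% | 7% |

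Simulating the first three rows gives 4% v 16%, 6% v 26% and 17% v 45%, the same within simulation error.

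**4. What the average gives up.** Suppose a difference of 0.20 SD exists only at month 12. The month-12 test has SE √(2 × 0.75/388) = 0.0622 and power Φ(0.20/0.0622 − 1.96) = 90%. The average sees 0.20/4 = 0.05 with SE √(2 × 0.375/388) = 0.0440, giving 21%. So the average should sit beside month 12 and not replace it.

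**5. Where the interview symptoms go.** Section 3.1 takes adverse event outcomes from the medical record and patient-reported outcomes from the telephone interviews, and Section 7.7 names administrative data. Visit-template symptoms can reach Section 7.7, because Sections 5.8, 6.3.4 and 10.5.1.2 make template items retrievable. No section does the same for interview symptoms. Template counts are also a weaker comparison: unmasked clinicians record them, at visits whose core number differs by arm (Table 1: at least 5 pharmacist follow-ups in TCM; at least 2 medical-provider follow-ups plus 8 behavioral visits in IPT).

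**The case against.** A reader might infer that symptoms are tested only at month 12, that withdrawal has gone by then, or that precipitated withdrawal would never appear in the results. The documents support none of these. The Section 7.5 model contains arm-by-visit terms, so earlier contrasts can be estimated; month 12 is the primary assessment, not the sole one. Section 7.7 compares other adverse events at each time-point and overall, by taper assignment, and the Section 10.5 definition of an adverse event is broad enough to include withdrawal. Rotation visits are documented on a template, and the DSMB receives a summary of all adverse events every six months (Section 10.3). No section gives a distribution of taper starts or a symptom duration; the 0% at month 12 above follows from assuming no starts after month 9.

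It is also fair to say that a common 12-month time-point, matching the primary outcome, is a legitimate choice. The averaged test is itself weak, and symptoms lasting 3 to 6 months may be generous: Section 2.2.3 says slow tapering can prevent withdrawal, and Section 5.6.3 reports of the traditional rotation method that "patients usually prefer tapering rapidly over 2-5 days, rather than discontinuing abruptly". For symptoms that short, quarterly interviews detect little under either contrast.

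What stands against this: the plan does not commit to testing or reporting the earlier visits, names no withdrawal endpoint in Sections 7.5 to 7.7, and does not send the masked interview data to the one section that would compare events at every visit.

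**Conclusion.** The point holds as a weakness in how a secondary safety outcome is summarised. No stated number is wrong. The month-12 contrast can miss temporary symptoms by timing and uses one visit of four; it does not average them away, since it averages over no visits. The gain from averaging rests on assumed taper uptake, timing, symptom size and duration: about 4–17% v 16–45% power for symptoms of 3 to 6 months with starts in months 1 to 9; 11% v 17% for 3-month symptoms if starts run to month 12; almost nothing for symptoms under a month. The documents do not state the recall period of the symptom items; a long recall period would change these figures. The change is worth making because it needs no new interviews, and with month 12 kept alongside nothing is lost.

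**What to change.** For adverse/physical symptoms only:

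- State in Section 7.5 that adverse symptoms, adverse effects and physical symptoms are the same measure, or give each its own analysis.
- From the same model, pre-specify the arm difference averaged over months 3, 6, 9 and 12, and report the month-12 contrast beside it. Do the same in Section 7.6 for expanded against standard options.
- Add the proportion worse than baseline at any interview, by arm and by taper assignment, with the threshold for worse fixed before unblinded data are seen.
- State in Section 7.7 whether interview and template symptoms count as other adverse events, and from which source.
- For participants who start buprenorphine, tabulate the withdrawal recorded at the 2-day, 1-week and 3-week visits with an exact interval, as far as the existing templates allow. This is descriptive: only those who choose rotation have these visits, so it is not a randomized comparison. Section 5.6.3 expects withdrawal before a traditional start, so expected and precipitated withdrawal need separate definitions if both are to be counted.

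The cost is SAP wording, one more contrast from a model already planned, a responder definition and a descriptive table. The averaged contrast is clearly less sensitive to a difference that appears only at month 12, which is why both are reported. Clinical management does not change.
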